Study Duration	The duration of the study for a subject is approximately 24 weeks, excluding the screening period.

Population	Sample Size The accrual objective is 116 subjects, 58 and 58 for the dupilumab and placebo treatment groups, respectively, with a history of confirmed milk allergy will be enrolled at 2 academic sites in the US. Target Population Male and female subjects aged 4 to 50 years, inclusive, with a history of cow's milk allergy confirmed by milk SPT and/or milk-specific IgE, and by the level of milk protein tolerated during DPBCFC to milk.
Treatment Description	Study Drug: Dupilumab - Dose/Route/Schedule 
 • Participants aged 4-5 years old: 
 ○ ≥ 5 to <15kg will receive dupilumab 200 mg or placebo SC every 4 weeks following a loading dose of 400 mg on day 1 (Visit 2) ○ ≥ 15 to <30kg will receive dupilumab 300 mg or placebo SC every 4 weeks following a loading dose of 600 mg on day 1 (Visit 2) ○ ≥ 30kg will receive dupilumab 300 mg or placebo SC every 2 weeks following a loading dose of 600 mg on day 1 (Visit 2) • Participants aged 6-17 years old: 
 ○ ≥ 15 to <30kg will receive dupilumab 300 mg or placebo SC every 4 weeks following a loading dose of 600 mg on day 1 (Visit 2) ○ ≥ 30 to <60kg will receive dupilumab 200 mg or placebo SC every 2 weeks following a loading dose of 400 mg on day 1 (Visit 2) ○ ≥ 60kg will receive dupilumab 300 mg or placebo SC every 2 weeks following a loading dose of 600 mg on day 1 (Visit 2) • Participants aged 18 years or older will receive dupilumab 300 mg of placebo SC every 2 weeks following a loading dose of 600 mg on day 1 (Visit 2) Placebo for Study Drug - Route/Schedule Placebo matching dupilumab is prepared in the same formulation as the active agent without the addition of protein (i.e., active substance, anti-IL-4R α monoclonal antibody). Background Treatment (Cow's Milk Protein) - Dose/Route/Schedule Cow's milk protein in powder form for oral use taken daily for 20 weeks: Initial dose at 5 to 20 mg protein daily, escalating every two weeks to 1000 mg daily

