Dupilumab, a fully human monoclonal antibody directed against interleukin-4 receptor alpha (IL-4R α), blocks the activity of IL-4 and IL-13 at both the type 1 and 2 receptor (Regeneron Pharmaceuticals, Inc. 2019, Sastre 2018). These receptors are present on a majority of the cell types involved in the induction and perpetuation of a Type 2 response, including B cells, eosinophils, macrophages, and basophils, and the binding of IL-4 and/or IL-13 has been shown to initiate a signal cascade that plays a critical role in modulating the expression of genes involved in both IgE class switching and Th2 cell differentiation. This pathway has been implicated in multiple atopic diseases via its ability to induce B Cell isotype class switching to allergen-specific IgE, Th2 cell proliferation, and proinflammatory cytokine production. Inhibiting both IL-4 and IL-13 signaling with dupilumab has demonstrated clinical efficacy in moderate-to-severe atopic dermatitis (AD), persistent, uncontrolled asthma, nasal polyposis, and is currently being investigated in eosinophilic esophagitis (EoE). It is known that oral allergen up-dosing during OIT induces up-regulation of IL-4 and IL-13 as well as other Type 2 inflammatory cytokines and pathway activity, which contribute to dose-limiting side effects of OIT such as GI (nausea, vomiting, diarrhea and abdominal pain), respiratory (wheezing and shortness of breath), and skin (generalized rash, pruritus, and angioedema) symptoms. By inhibiting the activation of IL-4R α , it is hypothesized that dupilumab may disable a number of signaling pathways involved in the development and progression of allergic responses.

This study will explore whether dupilumab has the ability to enhance immunomodulatory effects of OIT by decreasing Type 2 responses, decreasing production of milk-specific IgE, and potentially increasing the milk-specific IgG4 response, which will result in improved safety and tolerability of OIT up-dosing as well as improved efficacy as determined by the ability to tolerate a higher cumulative dose of milk protein during a double-blind, placebo-controlled food challenge (DBPCFC) after 18 and 24 weeks of therapy compared to placebo. In addition, the study will evaluate whether dupilumab influences known biomarkers important in the allergic response such as a reduction in allergen-specific immunoglobulin sub-class switching to IgE, decrease in basophil activation, and decreased Th2 cytokine levels.

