3.5.2. Secondary Endpoints

Clinical Endpoints:

- Comparisons of each treatment group for the following:
 - Proportion of participants who tolerate at least 1040 mg cumulative milk protein during DBPCFC at week 18
 - Proportion of participants who tolerate 4040 mg cumulative milk protein during DBPCFC at week 18
 - Proportion of participants who tolerate at least 1040 mg cumulative milk protein during DBPCFC at week 24

- Proportion of participants who tolerate at least 2040 mg cumulative milk protein during DBPCFC at week 24
- Proportion of participants who tolerate 4040 mg cumulative milk protein during DBPCFC at week 24
- Change in the cumulative tolerated dose (CTD) of milk protein during DBPCFC from baseline to week 18 and baseline to week 24 across cohorts as pairwise comparisons of all treatment groups.
- Due to the positive skew for the distribution of the CTD, a log transformation will be applied to reduce the skewness.

Safety Endpoints:

- The rate and severity of OIT-induced gastrointestinal symptoms in subjects receiving dupilumab compared to placebo.
- Proportion of participants who have OIT-induced gastrointestinal symptoms, dupilumab compared to placebo
- The rate and severity of AEs, serious adverse events (SAEs), and safety events in each cohort
- Proportion of participants completing the study among cohorts

Exploratory and Mechanistic Endpoints:

- Change from baseline to week 24 in the log-transformed minimum concentration of milk protein which activates basophils, comparison between dupilumab and placebo
- Percent change from baseline to week 24 in milk-specific and total IgE and milk-specific and total IgG4, comparison between dupilumab and placebo
- Percent change from baseline to week 24 in milk skin prick test (SPT) response, comparison between dupilumab and placebo
- Proportion of subjects experiencing esophageal eosinophilia, dupilumab compared to placebo, if data is available

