5.3. Risk-Benefit of Milk Protein OIT

Based on previously published studies, up to 95% subjects exhibit dose-related AEs during milk OIT, the majority of reactions presenting as mild and declining throughout dose escalation ([Vázquez-Ortiz 2013](#), [Martorell Calatayud 2014](#), [Mori 2017](#), [De Schryver 2019](#)). Approximately 25% of patients experience more severe reactions. Allergic symptoms may include sneezing, rhinorrhea, urticaria, angioedema, flushing, flares of eczema, ocular, nasal, oral and/or throat pruritus, nausea, vomiting, abdominal discomfort, stridor/laryngeal edema, cough, wheezing and/or shortness of breath, in addition to severe anaphylaxis.

The only major atypical AE reported in the literature related to OIT has been several reported cases of EoE ([Hill 2017](#), [Lucendo 2014](#), [Morais Silva 2014](#)). In adult patients with EoE, treatment with dupilumab has shown clinical improvement of symptoms and histology in phase II studies ([Sastre 2018](#)).

Oral food challenges may induce a severe life threatening allergic reaction; however, the risk can be greatly mitigated by conducting the challenges in a highly monitored setting and by initiating the challenge with a very small amount of the food, gradually increasing the dose, and stopping the challenge at the first sign of a reaction. If subjects develop an allergic reaction during the challenges, they may need oral, IM, or IV medications. Additionally, IV catheters may be placed, at clinician discretion for any visit, based on factors such as previous reactions, recent clinical history, and clinical status observed at the visit. Trained personnel, including a study clinician, as well as medications and equipment, will be immediately available to treat any reaction. The anticipated rate of life threatening anaphylactic reactions is <0.1%. There may be a risk that during the study subjects may decrease their vigilance against accidental food allergen ingestion because they believe they are protected from it. Therefore, subjects will be warned that they should continue to practice their usual vigilance against accidental ingestion of food allergens or food allergen-containing foods and reminded to carry their epinephrine auto-injector at all times.

The potential benefit of milk OIT to desensitize milk allergic subjects is outlined in **Section 1.2.1**.

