6.3. Assessment of Participant Compliance with Investigational Agent

Participants (and families) will document daily dosing and any reactions from at-home dosing on Dosing & Symptom Diary Logs. For milk OIT-related symptoms, participants will be reminded to report itching of the tongue or mouth; tongue/mouth/throat pain; lip/tongue/throat swelling; stomach pain; nausea/vomiting; nasal itching or congestion; runny nose; and hives around the mouth or face. For specific symptoms related to the study injection, participants will be reminded to report injection site pain, redness, tenderness, and swelling. Parents or caregivers should fill out the diary daily for children less than 12 years old. Children 12 years old and above may fill out the diary themselves with parent or caregiver supervision. Monitoring of compliance will be performed by reviewing the participant's diary and monitoring and counting their returned, unused study product. Unused milk OIT doses will be brought back to the clinic with each visit and collected by study staff for reconciliation of remaining doses.

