11.2.5. Adverse Events of Special Interest

An adverse event of special interest (AESI; serious or non-serious) is one of scientific and medical concern specific to the sponsor's product or program, for which ongoing monitoring and rapid communication by the investigator to the sponsor can be appropriate. Such an event might warrant further investigation in order to characterize and understand it. Depending on the nature of the event, rapid communication by the trial sponsor to other parties (e.g. regulators) might also be warranted.

AESIs for dupilumab or placebo in this study include the following:

- Life threatening anaphylactic reactions
- Systemic or extensive hypersensitivity reactions
- Malignancy
- Helminthic infections
- Suicide-related events
- Conjunctivitis (any type or etiology), keratitis or blepharitis (for all these AEs only events that are severe or serious or lasting ≥ 4 weeks will be reported as AESIs)

AESIs for milk OIT in this study include:

- Life threatening Anaphylactic reactions
- Gastrointestinal AEs resulting in prolonged disruption of dosing; gastrointestinal AEs include dysphagia, nausea, vomiting, abdominal pain, diarrhea, but exclude oral itching/tingling.

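### The home-diary reminder list leaves out diarrhea, lower-respiratory symptoms and generalized rash, all of which the protocol itself names as reactions to milk OIT

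*Combined protocol and SAP*

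**What the plan says.** Section 6.3 sets up the home diary with an open instruction: "Participants (and families) will document daily dosing and any reactions from at-home dosing on Dosing & Symptom Diary Logs". It then lists the milk-OIT symptoms that participants will be reminded to report. The list opens with itching of the tongue or mouth and pain in the tongue, mouth or throat, and continues: "lip/tongue/throat swelling; stomach pain; nausea/vomiting; nasal itching or congestion; runny nose; and hives around the mouth or face".

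Three other sections list OIT reactions:

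- Section 11.2.5, within the milk-OIT adverse events of special interest: "gastrointestinal AEs include dysphagia, nausea, vomiting, abdominal pain, diarrhea, but exclude oral itching/tingling".
- Section 1.1: "dose-limiting side effects of OIT such as GI (nausea, vomiting, diarrhea and abdominal pain), respiratory (wheezing and shortness of breath", followed by skin symptoms that include generalized rash.
- Section 5.3, among expected allergic symptoms: "stridor/laryngeal edema, cough, wheezing and/or shortness of breath".

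Section 3.5.2 includes this safety endpoint: "The rate and severity of OIT-induced gastrointestinal symptoms in subjects receiving dupilumab compared to placebo". Beside it stand the proportion of participants with such symptoms, and the rate and severity of AEs in general. No symptom list is attached to the gastrointestinal endpoint.

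Section 11.2.1 decides where a symptom is recorded. Expected, related symptoms within two hours of dosing are dosing reactions rather than AEs. Home episodes reach the AE or SAE form if they are Grade 3 or higher, or serious. Symptoms that occur more than two hours after dosing go on the AE form.

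**The concern.** A reminder list shapes what people write down. Where a protocol chooses to name symptoms, those left off depend more on unprompted reporting at home or on recall at a visit about two weeks later. Diarrhea is the clearest case, because the protocol calls it a gastrointestinal effect of OIT twice and prompts for it neither in the diary nor in the symptom list used at visits.

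This touches a stated aim. Section 1.1 says the protocol was designed to explore whether dupilumab reduces the number or severity of abdominal events. It also puts gastrointestinal symptoms at 40% of OIT subjects. A mild symptom that was not recorded at the time cannot be reliably recovered at analysis. The missing respiratory and generalized skin prompts raise the same question for a different endpoint, the rate and severity of AEs in general.

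**Working it through.** The plan gives no figure to reproduce. The check is a comparison of lists, a count of home dosing days, and a trace of the recording routes.

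**1. The lists side by side**

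| Symptom | Named as an OIT effect in | Section 6.3 reminder | Section 6.4 every-visit list |
|---|---|---|---|
| Nausea, vomiting | 1.1, 5.3, 11.2.5 | yes | yes |
| Abdominal pain | 1.1, 11.2.5 | yes (stomach pain) | yes |
| Dysphagia | 11.2.5 | no | yes |
| Diarrhea | 1.1, 11.2.5 | no | no |
| Wheeze, shortness of breath | 1.1, 5.3 | no | no |
| Cough | 5.3 | no | no |
| Generalized rash | 1.1 | no (hives at mouth or face only) | no |

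The reminder list covers 3 of the 5 gastrointestinal terms in Section 11.2.5. With the visit list added, 4 of 5 are covered and only diarrhea remains. The Section 6.4 list is aimed at eosinophilic esophagitis, so it would not be expected to hold respiratory or skin terms.

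**2. Share of OIT dosing days at home**

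Inputs: the synopsis gives OIT as daily for 20 weeks; Table 4 gives the visits; Section 8.3 has the home dose withheld on in-clinic dosing days and challenge days.

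- Days from week 4 to week 24: (24 - 4) x 7 = 140.
- In-clinic OIT doses at V4 to V10, V12 and V13: 7 + 2 = 9.
- Challenge days without a home dose, assumed to be 2 to 4 in this window: home doses = 140 - 9 - 2 = 129, down to 140 - 9 - 4 = 127.
- Home share of OIT dosing days: 129 / (129 + 9) = 93.5%, or 127 / (127 + 9) = 93.4%.
- To week 18 only: (18 - 4) x 7 = 98 days with 7 in-clinic doses, so 91 / 98 = 92.9%.

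The share is about 93% either way. It assumes nominal visit dates and no missed doses.

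**3. Who first learns of a mild home symptom**

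- Moderate or severe allergic symptoms: Section 5.6.1 asks the family to call the site.
- Grade 3 or higher, or serious: AE or SAE form (Section 11.2.1).
- Expected, Grade 1-2 and within two hours: dosing reaction, not an AE (Section 11.2.1). If mild, no call is requested.
- More than two hours after dosing: AE form, but someone must first report the symptom.

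For mild symptoms, the diary and the visit interview are what remain. Section 11.4.2 permits a checklist or structured questioning but does not say what it contains. Section 13.6.1 describes summaries of AEs and does not mention dosing reactions.

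**4. Direction of any effect**

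Suppose the same fraction s of cases is captured in both arms. The observed difference in proportions is then s x (p_placebo - p_dupilumab). The difference shrinks by the factor s, and the ratio of proportions is unchanged. The proportion endpoint is less exposed than the rate endpoint, because a participant with diarrhea who also reports stomach pain, nausea or vomiting is still counted. The value of s cannot be estimated: the documents give no frequency for diarrhea during home OIT and no sensitivity for the diary.

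**The case against.** The strongest reply is that the diary asks for any reaction, and the list is only a reminder placed in a section on compliance. The diary form is not among the appendices and the Manual of Procedures is not available, so what the form itself prints cannot be seen. AEs are also collected at every visit, and the Section 6.4 list is introduced as examples rather than as complete. All of this stands. It is why the conclusion is a risk of under-reporting and not a demonstrated loss.

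A reader might infer four stronger things that the documents do not support.

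- *That two of five terms missing means 40% of gastrointestinal events are lost.* That is a share of words in a list, not of events. Dysphagia is largely covered by the every-visit monitoring and by the PEESS or EEsAI questionnaires at Visits 2, 4, 10 and 14a.
- *That missing respiratory prompts weaken the gastrointestinal endpoint or the up-dosing decision.* They cannot affect a gastrointestinal endpoint. Sections 6.4 and 8.3 place a physical examination and lung function assessment before each escalation.
- *That Section 11.2.5 defines the endpoint.* It defines an event of special interest, namely gastrointestinal AEs with prolonged disruption of dosing. The endpoint has no list of its own, which is a reason to give it one.
- *That the arms are biased against each other.* The diary is the same in both blinded arms. Section 5.2 lists diarrhea as a dupilumab reaction in two other indications. That is a reason to measure it well, not evidence of differential capture.

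Prompting for mouth itching is not a fault either, since it is an OIT reaction relevant to the allergic-AE objective.

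**Conclusion.** The mismatch between the Section 6.3 reminder list and the protocol's own lists of OIT reactions is real and can be read directly from the text. Its consequence is limited. Mild diarrhea at home is at risk of under-reporting for the gastrointestinal safety endpoints. Mild lower-respiratory or generalized skin reactions at home are at risk for the general AE endpoint. It would go too far to say that the gastrointestinal endpoint is under-recorded, because the open diary instruction and the visit interviews may catch what the list omits.

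The 93% figure shows where doses are taken, not how much is missed. If capture is incomplete to the same degree in both arms, absolute rates would be too low and a difference would tend to be diluted. Neither the primary endpoint nor the secondary endpoint tested hierarchically under Section 13.5.4 is affected. The conclusion assumes that the diary and visit questioning follow the lists in the protocol. A diary form or Manual of Procedures that already prompts for these symptoms would largely remove the concern.

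**What to change.** Add diarrhea, difficulty swallowing, cough, wheeze, shortness of breath, and generalized hives or rash to the Section 6.3 reminder list and to the diary form.

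In Section 3.5.2, build the gastrointestinal endpoint from the five Section 11.2.5 symptom terms, with oral itching reported separately. State that it draws on both the dosing-reaction records and the AE form, so that early mild home reactions are not lost because of where they are recorded.

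The cost is a short protocol edit, a revised diary page and a slightly longer daily entry. If the trial is already running, the new form should be introduced in both arms equally and its date recorded, so that reporting before and after the change can be told apart. No dose or treatment rule changes.

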6.4. Toxicity Prevention and Management

Potential risk of fever, arthralgia, and rash due to biologics (Dupilumab)

Some omalizumab-treated participants have experienced arthritis/arthralgia, rash, fever and lymphadenopathy with an onset 1 to 5 days after the first or subsequent injections of omalizumab. These signs and symptoms, similar to those observed in patients with serum sickness due to biologics (monoclonal antibodies), have recurred after additional doses in some patients. Investigational product will be discontinued if a participant develops these signs and symptoms.

Potential risk for eosinophilic conditions

- Subjects will be actively monitored for early development of EoE by monitoring for symptoms at each study visit such as gastroesophageal reflux, nausea, vomiting, abdominal pain, dysphagia, choking or gagging with meals, and food impaction. At Visits 2, 4, 10, and 14a, the validated Pediatric Eosinophilic Esophagitis Symptom Score (PEESS) v2.0 ([Franciosi 2011](#)) or Eosinophilic Esophagitis Activity Index (EEsAI) ([Schoepfer 2014](#)) questionnaires will be administered to assist with characterization of EoE in children and adolescents or adults, respectively.
- For chronic/recurrent GI symptoms, especially upper GI symptoms, the investigator will refer to a GI specialist for evaluation of suspected EoE when:
 - Any participant withdraws OIT dosing for ≥ 7 days due to GI AEs and is still having GI AEs

- Any participant who develops chronic/recurrent GI AEs as defined by experiencing symptoms for >6 weeks despite dosing adjustments and use of proton pump inhibitors

Potential risk for injection site reactions (ISR) persisting longer than 24 hours

Based on the SC mode of administration as well as a higher incidence of local ISRs observed for dupilumab in general, severe ISRs lasting longer than 24 hours are considered as a potential risk. Any severe ISR that persists longer than 24 hours will be recorded.

Potential risk for drug-drug interactions

The clinical significance of the limited in vitro findings for IL-4 and IL-13 involvement in the CYP regulation reported in the literature, and the impact of dupilumab on CYP enzymes are not fully understood. As a precautionary measure, during the study treatment and up to the end of follow-up, caution should be used for drugs with a narrow therapeutic index that are metabolized via the CYP isoforms. The Investigators are advised to use close clinical observation and/or laboratory monitoring, as applicable, to enable early detection of potential toxic manifestations or lack of activity/efficacy of these narrow therapeutic index drugs, followed by dose adjustment or withdrawal if needed.

Reactions to OIT during the initial dose escalation

Participants may develop symptoms during the initial escalation at Visit 4. A study clinician trained in the protocol will be present on the unit floor. The investigator's judgment will be required to determine the best course of action with possible actions being:

1. Extend time interval between dosing (up to an additional 30 minutes)
2. Discontinue with any further escalation

The escalation may be stopped at the occurrence of any AE per clinician discretion. All subjects will be observed for a minimum of 2 hours following administration of the final dose and will be discharged only when deemed clinically stable by a study clinician.

Reactions to OIT during Combination Therapy or Washout Phase

Participants will undergo physical examination with lung function assessment prior to OIT dose escalation to determine it is safe to escalate the dose. Per investigator discretion and the Manual of Procedures, subjects may be maintained on their current dose of OIT, or down-dose, depending on their tolerance of the current dose and health status. Participants will be observed in clinic following all in-clinic OIT dosing according to the minimum observation periods specified by the Manual of Procedures and discharged only when the participant is deemed clinically stable per the supervising clinician.

If, at any point in the study, the subject complains of new onset vomiting, dysphagia, chronic abdominal pain, and/or difficulty swallowing for more than 2 weeks despite use of daily antacids (<https://www.webmd.com/heartburn-gerd/qa/what-are-examples-of-antacids>), the subject will be given daily proton pump inhibitors (PPIs) (dosed per age and weight) <https://medlineplus.gov/ency/patientinstructions/000381.html> and, if no relief occurs in 2 weeks, they will be referred to a gastroenterologist for assessment of possible gastroenterological disorders associated with food allergy (i.e. EoE). If at any point side effects

develop from the use of antacids or PPIs, the subject will be discontinued on the concomitant medication and referred to a GI specialist.

For specific questions related to dosing escalation or continuation of the same dose that are not answered in the above protocol, the Investigator will be available for questions and decision-making.

